### **3. STUDY DESIGN**

#### **3.1. DESCRIPTION OF STUDY DESIGN**

This multi-center, randomized, double-blind, three-arm, parallel-group trial is designed to assess the efficacy and safety of two doses (4 IU/kg/day and 8 IU/kg/day) of NTRA-9620 compared to matching placebo at two time points (12 and 24 weeks post randomization) administered to infants less than 52 weeks chronological age with SBS (following surgical resection). The study will be conducted at up to 40 clinical trial sites in North America, Europe and Israel. All subjects will be enrolled after their parent(s) or legally authorized guardian(s) sign an IRB/IEC approved informed consent form (ICF). Subjects entering the study will be diagnosed with SBS; they will have at most 70% of their expected bowel length preserved or functioning, requiring PN by intravenous (IV) infusion; they will have a total body weight of at least 500 grams (17.6 ounces) and be at least 28 weeks of gestation in age at the time of entry into the study. At time of study entry, subjects should be able to tolerate at least 10 mL/kg/day of EN but not less than 70% of PN based on caloric intake for at least 7 days.

Each subject, after parent(s) or legal guardian(s) consent to the study, will complete screening assessments. Screening evaluations will include assessment of entry criteria, medical history, as well as a complete physical examination, blood chemistry, hematology and urinalysis evaluations, EKG and concomitant medications.

After meeting all screening and baseline criteria, subjects will be randomized in a 1:1:1 ratio to either 8 IU/kg/day NTRA-9620, 4 IU/kg/day NTRA-9620, or matching placebo. Randomization, which will be performed centrally, will be stratified by estimated percent length of the remaining small intestine ( $L < 50\%$  or  $50\% \leq L \leq 70\%$ ; where L is remaining length of small intestine relative to the expected length for gestational age (13)) and presence or absence of an ileocecal valve. Randomization will take place as close as possible to treatment initiation and not more than 24 hours before the first dose of study medication.

During the 24-week treatment period, subjects are expected to be on PN/IV for all or most of the treatment period and thus are expected to be hospitalized for approximately 12 weeks, but they may be released sooner according to local institution's SOC.

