### **8.1.1. Interim Check of Variance Assumption**

This multicenter trial will allow inclusion of a large population of infants from preterm to one year, SBS of varying etiologies, bowel length of varying sizes, presence or absence of ileocecal valve, and varying feeding regimes (e.g., formula only, full or partial own mother's milk). We know of no similar study that has been conducted in such a wide-ranging population - a population that is expected to have especially high variation with respect to prognosis and therefore to study outcome. Our best estimate of within-group variation, which is critical for accurately computing study power, is based on a small pilot study in a related, but not identical, indication. Consequently, we will assess the assumptions used for calculating power by computing the common pooled standard deviation of percent change in %PN when 75 subjects have completed 12 weeks in the study. Should the calculated standard deviation be at least 22% (i.e., 10% greater than the 20% assumed in the protocol), sample size may be adjusted upward accordingly. A statistician blinded to group assignment will compute this interim standard deviation. That statistician will not be involved in any other aspect of the trial. The sponsor will decide whether to increase the sample size during the trial; the decision will be based on the estimated variance but without any knowledge of the interim effect size.

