### **8.1.2. Statistical Tests of Co-Primary and Key Secondary Endpoints**

#### **Co-Primary Endpoint (means)**

The two endpoints (12 weeks and 24 weeks) will each be analyzed using an analysis of covariance model with PC\_PN0-12 and PC\_PN0-24 serving as the dependent variable for each respective analysis. Treatment group and the randomization stratification variables will serve as factors and the baseline %PN value will serve as a covariate in each analysis. In each analysis, the higher dose group will be compared to placebo group first. The high-dose comparison will be tested at the 0.025 two-sided significance level at each timepoint. If the high-dose comparison at a particular timepoint is significant at  $p < 0.025$ , then the low-dose comparison with placebo (at the same timepoint) will be tested at the 0.025 level.

For this endpoint, the Type I error rate will be controlled at 0.05 by using a Bonferroni correction for the two timepoints and a step-down procedure to compare each dose group (high dose first, then low dose) with placebo.

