#### **8.4. SAMPLE SIZE**

The sample size is based on testing the superiority of the high dose of NTRA-9620 compared to placebo on the primary endpoints of percent change in %PN from baseline to time “t” (PC\_PN0-t) where “t” = 12 and 24 weeks. On the basis of historical data, the assumed reduction in PC\_PN0-t is 30% and 42% in placebo and NTRA- 9620, respectively, at both 12 and 24 weeks. A common within-group standard deviation of 20% has been assumed for both arms.

Given the above specifications, and based on the use of a two-sided, two-sample comparison of means at the alpha = 0.025 level of significance, a sample of 45 subjects per group would provide approximately 80% power to demonstrate superiority. Since some subjects may not complete the entire trial, an additional 10% of subjects will be enrolled per arm (50 subjects per arm) to account for this potential loss. Thus, the proposed sample size is 150 subjects.

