#### **8.5. STATISTICAL ANALYSIS**

##### **8.5.1. Overview**

Safety and Full Analysis Set (FAS) will be conducted on the safety analysis set. Primary and key secondary efficacy testing will be done using the FAS and the mITT sets. Efficacy testing, including primary and key secondary endpoints, may also be performed on the PP set.

The data will be summarized by group and overall. For continuous data, tables will present means, standard deviations, medians, minima, maxima, appropriate percentiles, and number of

subjects. For categorical data, tables will show counts and percentages. “Time-to-event” data will be summarized using the Kaplan-Meier method. Data listings by subject will be provided.

Statistical analyses will generally be performed using the SAS® system. The effects of noncompliance, dropouts, and possible covariates such as gestational age, birth weight and gender will be assessed as sensitivity analyses.

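### The primary ANCOVA omits age and uses bowel length only as two classes, although Section 8.1.1 names both as sources of prognostic variation: a near-free efficiency gain of unknown size

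*Combined protocol and SAP*

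**What the plan says.** Section 8.1.2 of the protocol sets the primary model: "Treatment group and the randomization stratification variables will serve as factors and the baseline %PN value will serve as a covariate in each analysis". Section 8.5.5.1 and the synopsis say the same. The strata (Sections 3.1 and 4.2.3) are remaining small-bowel length, below 50% or 50-70% of expected, and ileocecal valve present or absent.

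Section 8.5.1 leaves the rest to secondary status: "possible covariates such as gestational age, birth weight and gender will be assessed as sensitivity analyses". Section 8.5.3 does likewise for baseline variables that turn out to differ between arms.

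Section 8.1.1 describes the infants as "a population that is expected to have especially high variation with respect to prognosis and therefore to study outcome". The sources it lists are age from preterm to one year, etiology, bowel length, ileocecal valve and feeding regime.

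Section 8.1 says that a full SAP, written while the study is blind, will prevail over the protocol. That text is not in the documents.

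**The concern.** Power for a comparison of means depends on the residual variance. A pre-specified baseline covariate that predicts outcome lowers that variance without bias and without more patients. Here the plan itself names age and bowel length as reasons for a wide spread in outcome, yet the primary model has no age term and one cut in bowel length. The lower class puts very short remnants together with 49%.

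The information is already at hand. Age and percentage of bowel remaining are needed to check inclusion criteria 1 and 4, and the percentage is needed to assign the stratum.

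Precision matters more because, as Step 2 below shows, the sample size does not deliver its stated power at the stated alpha.

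**Working it through.** **Step 1. Sources of variation named in Section 8.1.1 against the primary model.**

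| Named in 8.1.1 | In the primary ANCOVA |
|---|---|
| Age, preterm to one year | No |
| Etiology | No |
| Bowel length | Only as <50% or 50-70% |
| Ileocecal valve | Yes |
| Feeding regime | No |

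Baseline %PN is also in the model. Time from resection and ostomy status are known from inclusion criteria 7 and 4, but Section 8.1.1 does not name them.

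**Step 2. The plan's own power figure.** Inputs from Section 8.4: the assumed reduction "is 30% and 42% in placebo and NTRA- 9620, respectively, at both 12 and 24 weeks", so the difference is 42 − 30 = 12 points; "A common within-group standard deviation of 20% has been assumed for both arms"; and a calculation "based on the use of a two-sided, two-sample comparison of means at the alpha = 0.025 level of significance". From Section 3.1, "subjects will be randomized in a 1:1:1 ratio". The claim is that "a sample of 45 subjects per group would provide approximately 80% power to demonstrate superiority".

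- Standard error = 20 × √(2/45) = 4.216.
- Noncentrality = 12 / 4.216 = 2.846.
- With 88 degrees of freedom and two-sided alpha 0.025, the critical t is 2.280.
- Power = 71.4% by noncentral t (72.7% by the normal formula).

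The stated 80% is not reproduced. It matches two-sided alpha 0.05, which gives 80.4%. At alpha 0.025, 80% needs 55 per arm (53 by the normal formula).

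**Step 3. Effect of explained variance.** Residual SD = 20 × √(1 − R²). The documents give no R²; 0 to 0.30 is an assumed range. 45 per arm, alpha 0.025, noncentral t with 88 degrees of freedom:

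| Assumed R² | Residual SD | Noncentrality | Power |
|---|---|---|---|
| 0 | 20.0 | 2.846 | 71.4% |
| 0.10 | 18.97 | 3.000 | 76.3% |
| 0.20 | 17.89 | 3.182 | 81.5% |
| 0.30 | 16.73 | 3.402 | 86.7% |

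**Step 4. What counts as gain.** The first row is an unadjusted two-sample test, not the planned ANCOVA. If the present terms explain a share E and new covariates explain a share A of what is left, the residual SD is 20 × √((1 − E)(1 − A)). Both shares are assumptions.

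- E = 0.10, A = 0.10: SD falls from 18.97 to 20 × √0.81 = 18.0, and power rises from 76.3% to about 81%.
- E = 0.20, A = 0.10: SD falls from 17.89 to 20 × √0.72 = 16.97, and power rises from 81.5% to about 86%.
- A = 0: no gain, whatever E is.

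**Step 5. Cost if the covariates are useless.** The three-arm ANCOVA has 135 − 3 − 2 − 1 = 129 error degrees of freedom. Four extra covariates leave 125, and power at SD 20 stays at 71.8% to one decimal. Chance imbalance in the added covariates inflates the variance by roughly 127/123 = 1.033 on average, which costs about 1.5 points of power. Four covariates therefore break even at an added R² of about 1 − 123/127 = 3%; two need less.

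**The case against.** The strongest case against is that nothing here is wrong. The plan uses a standard, valid ANCOVA that already contains two of the five sources named in Section 8.1.1 plus baseline %PN. No passage calls any omitted variable strongly prognostic; Section 8.5.1 calls its three candidates only possible covariates. High variation in outcome does not show that age or bowel length explains it, and continuous length overlaps with the length stratum. All of this stands. It makes the gain unknown and possibly close to zero.

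Four further limits also stand:

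- The sentence in Section 8.5.1 concerns gestational age, birth weight and gender, not the exact variables proposed below. It shows where the plan puts further adjustment, not that these variables were considered and rejected.
- Success requires both co-primaries at the same timepoint (Section 8.1.2), and the Mann-Whitney test is unadjusted. Its one-sided 0.10 threshold is looser, so the ANCOVA is probably the harder test, but the gain in overall success may be smaller than the table suggests.
- Uncertain variance already has a remedy in the blinded SD check of Section 8.1.1.
- The prevailing SAP may deal with covariates.

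A reader might also infer that the primary analysis is biased, or that added covariates would bring the trial back to 80%. The documents support neither. Randomization protects the planned comparison, and a shortfall in Section 8.4 cannot be repaired with an R² that nobody has estimated.

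What survives is narrow: two variables that the plan itself names and already needs for eligibility are missing from the primary model or coarsened, and including them costs almost nothing.

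**Conclusion.** The point holds as a missed gain in efficiency, not as an error or a bias. Age is absent from the primary ANCOVA and bowel length is cut once at 50%, against Section 8.1.1's own list of prognostic sources.

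From the unadjusted 71.4%, assumed explained variance of 10, 20 or 30% gives 76.3, 81.5 or 86.7%. These figures rest on the inputs of Section 8.4 and on 45 evaluable infants per arm. The true gain is only the part beyond the strata and baseline %PN, and may be nil. The likely downside is about 1.5 points at most for up to four covariates.

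The failure of Section 8.4 to reproduce 80% at alpha 0.025 is a separate finding, whatever covariate list is chosen.

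**What to change.** Before unblinding, amend Sections 8.1.2 and 8.5.5.1, the synopsis and the SAP so that the primary ANCOVA contains, besides the present terms:

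- post-menstrual age at randomization, continuous;
- remaining small-bowel percentage, continuous.

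Time from resection to randomization and ostomy in place (yes/no) are optional additions, to be justified on clinical grounds because Section 8.1.1 does not name them. Fix the list in advance, keep the present model as a sensitivity analysis, and state in Section 8.5.3 that observed imbalance will not decide the primary covariates. Carry the same covariates into the imputation model of Section 8.1.3.

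The cost is SAP wording and two to four degrees of freedom, with no new assessment. Confirm that the case report form keeps the bowel percentage itself and not only its class. Correct the power statement in Section 8.4 separately, without crediting any covariate gain unless there is evidence on R².

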#### **8.5.2. Subject Disposition**

Subject disposition will be tabulated; the number of subjects enrolled, exposed, prematurely terminated from study drug, prematurely terminated from study, and completed will be summarized by treatment group and overall. A list of dropouts will be prepared including reason for, and time of, discontinuation.

#### **8.5.3. Demographic and Baseline Characteristics**

Subjects in each treatment arm will be characterized using tables, figures, and descriptive statistics for demographic and baseline clinical variables. Treatment groups will be compared to evaluate the balance achieved by randomization. Observed differences between the groups, should there be any, will be interpreted for their clinical significance and their potential use as covariates in sensitivity analyses of the analysis of efficacy endpoints.

#### **8.5.4. Safety Analysis**

The safety analyses will be descriptive and narrative in nature, with SAEs and AEs coded using MedDRA and tabulated by body system, preferred term, treatment group, severity and relation to procedure. Descriptive statistics will be provided by treatment group as appropriate.

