#### **4.1.2. Medical History and Demographics**

The subject's medical history will be fully documented at screening to ensure compliance with study eligibility criteria. Medical history information must include, but not be limited to, past and present medical conditions, concomitant non-drug treatments and hypersensitivity to drugs. Any event that occurs before study drug dosing will be recorded as medical history.

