#### **4.1.13. Adverse Events (AEs)**

The information obtained during study visits, physical examinations, vital signs measurements, blood testing, and by any other means will be evaluated in light of baseline medical data and thus provide the basis for identification and grading of AEs.

The AEs reported during the trial will be graded (see Section [7.1](#)), documented, and assessed in light of their clinical significance and relation to investigational product. In addition, the following information regarding the AE must be obtained and recorded in subject's source document and Case Report Form (CRF): AE description, start date, end date (if applicable) or ongoing, severity, seriousness, investigator's assessment of the relationship of the AE to study drug, outcome (i.e., resolved, resolved with sequelae, ongoing, death due to this AE, death due to other events, unknown) and action taken (e.g., concomitant medication). Information regarding occurrence of AE monitoring will be captured throughout the study, from Day 7 (initiation of dosing) 28 days after the final primary study visit at Week 28 (Day 196). AEs considered treatment related by the Investigator will be documented after the primary study completion on Week 52 (Day 364) and Week 104 (Day 728) to assess any potentially related adverse outcomes of treatment and re-hospitalizations. Pre-treatment emergent events will not be considered as AEs, but will be recorded as medical history.

Prior to this current trial, four clinical trials including three in preterm infants and one in SBS infant subjects have been performed with oral administration of insulin. No treatment-related adverse events have been reported and no systemic absorption of insulin has been detected.

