#### 7.1.1. Definition of Adverse Events

##### **Adverse Event (AE)**

An adverse event (AE) is any untoward medical occurrence in a clinical investigation of a subject administered a pharmaceutical product (either test product or control product); an AE does not necessarily have a causal relationship with the treatment. An AE is therefore any unfavorable and unintended sign, symptom, or disease temporally associated with the use of an investigational (medicinal) product or other protocol-imposed intervention, regardless of attribution, i.e., whether or not related to that investigational (medicinal) product. An AE may include intercurrent illnesses or injuries that represent an exacerbation (increase in frequency, severity, or specificity) of pre-existing conditions (e.g., worsening of asthma). A laboratory abnormality will be reported on the “Adverse Event” case report form only if the investigators considered it clinically significant, or if it is associated with clinical sequelae or requires therapeutic intervention.

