##### **Unexpected AE**

An unexpected AE is one of a type not identified in nature, severity, or frequency in the current Investigator’s Brochure or of greater severity or frequency than expected based on the information in the Investigator’s Brochure.

A pre-treatment emergent event will not be considered an AE, but will be recorded as medical history.

Whenever possible, it is preferable to record a diagnosis as the AE term rather than a series of symptoms relating to a diagnosis. AEs will be graded according to the CTCAE v 4.03 ([Appendix C](#)). For events where the specific definitions for grading in CTCAE does not apply to this study population, general grading criteria described in CTCAE will be used and investigator judgment on severity will determine the grade of the event.

AEs monitoring will be captured throughout the study, from Day 0 (initiation of dosing) until final primary study visit at Week 28 (Day 196). Long-term safety evaluations will also be conducted post primary study completion on Week 52 (Days 364) and Week 104 (Day 728) to assess any potentially related adverse outcomes of treatment.

If an unrelated AE remains unresolved after Week 28, at the Investigator's discretion, the subject may be followed until Week 104, or until resolution of the event. The investigators must follow a related AE and any unrelated/related SAE until resolution even if the time extends beyond the study-reporting period. Resolution is defined as the return to baseline status or stabilization of the condition with the expectation that it will remain chronic; it is not a discharge date from the hospital.

The investigator will assess AEs for severity, for relationship to the study drug, and as to whether the event meets one or more of the definitions of an SAE.

The investigator will determine the relationship of an AE to the study drug and will record it on the source documents and AE CRF, using the categories defined below.

Causality Category	Description
Unlikely	A clinical event, including laboratory test abnormality, with a temporal relationship to drug administration which makes a causal relationship improbable, and in which other drugs, chemicals or underlying disease provide plausible explanations. For the purpose of this protocol, the term unlikely will be considered not related to study medication and an "Adverse Event".

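### The safety tables are classified by relation to procedure, which the plan neither defines nor provides for recording, and they omit relation to study drug, which is recorded

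*Combined protocol and SAP*

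**What the plan says.** **Tables.** Section 8.5.4 describes the safety analysis as descriptive and narrative, with coded AEs and SAEs "tabulated by body system, preferred term, treatment group, severity and relation to procedure". The Safety Analysis row of the synopsis uses the same classifiers. Neither lists relationship to study drug.

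**Causality.** Section 4.1.13 lists what must be recorded for each AE and includes the investigator's "assessment of the relationship of the AE to study drug". Section 7.1.1 repeats this: "The investigator will determine the relationship of an AE to the study drug and will record it on the source documents and AE CRF". The categories that follow are unlikely, possible and probable, each defined by the event's relation to the drug.

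**Events before dosing.** Section 4.1.2 states: "Any event that occurs before study drug dosing will be recorded as medical history". Section 7.1.1 states: "A pre-treatment emergent event will not be considered an AE, but will be recorded as medical history". Section 4.1.13 and Appendix B footnote p say the same in substance.

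**The concern.** A safety table needs a classifier that is defined and recorded. Relation to procedure is neither in this document. The product is an oral powder for reconstitution, so the word has no obvious referent. It could mean the bowel resection, a later operation, or a study procedure such as a blood draw. Two programmers working from Section 8.5.4 could build different tables, or find that they have no variable to build one from.

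The omitted variable matters more. Evaluating safety is part of the primary objective, and drug-relatedness runs through the rest of the safety system. It enters the criteria for stopping study medication (Section 5.2), several of the DSMB referral triggers (Section 5.4) and the SAE reporting clock (Section 7.2.1, 24 hours if related and 48 hours if not). It also determines which AEs are documented at Weeks 52 and 104 (Section 4.1.13). A report that followed Section 8.5.4 literally would not show that variable by arm.

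The second question is whether a serious event between consent and first dose counts as an SAE for reporting, since the general rule files pre-dose events as medical history.

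**Working it through.** No arithmetic applies, so this is a comparison of sections.

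**1. Classifiers specified against causality recorded.**

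| Place | Relation to procedure | Relation to study drug |
|---|---|---|
| Synopsis, Safety Analysis (tables) | specified | absent |
| Section 8.5.4 (tables) | specified | absent |
| Section 4.1.13 (AE items to record) | absent | required |
| Section 7.1.1 (source documents, AE CRF, causality categories) | absent | required, three categories |

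Two of the two places that specify the tables use relation to procedure, and none of the two uses relation to study drug. The two places that set causality recording show the reverse. The variable specified and the variable recorded do not overlap.

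**2. Could the stated table be derived from what is recorded?** The three categories grade the likelihood that the drug caused the event. An event graded unlikely may be due to underlying disease, another drug, surgery or anything else, so a procedure relationship cannot be recovered from the grade.

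**3. Could the omitted table be produced?** Yes. Drug causality is recorded for every AE, so a table by arm needs no new data.

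**4. Pre-dose events: the texts that pull apart.**
- Towards medical history only: Sections 4.1.2, 4.1.13 and 7.1.1 and Appendix B footnote p. Section 7.1 also limits collection to treatment-emergent AEs, and the AE definition in 7.1.1 opens with "any untoward medical occurrence in a clinical investigation of a subject administered a pharmaceutical product", which an undosed infant is not.
- Towards reporting: the same definition goes on to cover an event "temporally associated with the use of an investigational (medicinal) product or other protocol-imposed intervention, regardless of attribution". Section 7.2 defines an SAE over the course of the clinical investigation, not only after dosing. Section 7.2.1 requires all SAEs to go to the Sponsor. Section 8.3.1 counts AEs and SAEs at any time in the trial or follow-up.

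One reading is that a pre-dose event is not an AE and so cannot be an SAE. The other is that the SAE definition stands on its own. The document does not choose between them.

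**5. A neighbouring conflict.** AE capture starts at Day 0 in Section 7.1.1 and Appendix B footnote p, but at Day 7 in Section 4.1.13. Each is labelled as the initiation of dosing.

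**The case against.** The strongest reply is that the table wording is an editorial slip of little consequence. Section 8.1 says that Section 8 only outlines the analyses, that a full SAP will be written while the study is blind, and that the SAP prevails where the two differ. AEs and SAEs are still tabulated by arm and severity, which is the main safety comparison in a randomized double-blind trial. Section 5.4 also gives the DSMB unblinded summaries in which event rates are compared between groups.

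Most of this stands as a limit on the consequence. It does not remove the error. Sections 8.5.5.3, 8.5.6 and 8.5.7 expressly leave their content to the SAP, whereas Section 8.5.4 states its own rule. No later SAP safety text is in the document, so this wording is the specification on record.

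Four stronger readings are tempting and are not supported:

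- **Relation to procedure is never collected.** The CRF and SAE form are not in the document. What can be said is that the text does not provide for collecting it.
- **Drug-relatedness is lost.** It is recorded for every AE. Only its tabulation is unspecified.
- **A serious pre-dose event caused by a study procedure is never reported.** Sections 7.2 and 7.2.1 can be read to require reporting. Section 10.5 separately requires unanticipated problems involving risk to go to the IRB/IEC and the Sponsor. A pre-dose event that worsens after dosing counts as treatment-emergent under Section 7.1. Given its opening words, the AE definition does not settle the matter the other way.
- **Fourteen to 30 days of study blood draws are affected.** Section 4.2.2 places the citrulline and antibody samples on the last day of baseline only. The items it lists for daily recording are measurements, vital signs, feeding intolerance, medications and nutrition intake. The 30 days in Section 4.1.1 is how early consent may be signed, not a period of procedures.

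**Conclusion.** The table specification is wrong as written. Both places that specify the safety tables use a classifier that is undefined and not provided for, and both omit the one causality variable the protocol requires. The error touches the causality breakdown for all of about 150 infants. Its consequence is limited, because the data for the right table are recorded and the comparisons by arm and severity are unaffected. It is a specification error to correct, not a threat to the trial's safety conclusions.

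The pre-dose question is an ambiguity to reconcile. The documents do not show that any SAE report would be missed, and they give no event rate from which to size the issue.

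This rests on two assumptions: that the CRF follows the items listed in Sections 4.1.13 and 7.1.1, and that no later SAP text has already replaced Section 8.5.4. If either is false, the remaining work is to bring the protocol wording into line.

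**What to change.** **Main change.** In Section 8.5.4 and the synopsis, replace *relation to procedure* with *relation to study drug (unlikely, possible, probable)*. If a procedure relationship is also wanted, define which procedures count and add the assessment to Sections 4.1.13 and 7.1.1.

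**Reconciliation.** Make Sections 4.1.2, 4.1.13, 7.1, 7.1.1, 7.2, 7.2.1 and 8.3.1 and Appendix B footnote p agree on whether a serious event between consent and first dose is reported as an SAE. If it is, say where it is listed: the safety analysis set in Section 8.2.1 contains only infants whose treatment was initiated, so an infant never dosed would need a separate listing. The Day 0 and Day 7 start of AE capture should be aligned in the same edit.

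**Cost.** The main change is one phrase in two places. It needs no new visit, sample or data item and leaves the efficacy analysis untouched. The reconciliation is also wording. If it settles on reporting pre-dose SAEs, the added burden is whatever such reports arise, a number the documents do not allow one to estimate.
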